## 3. STUDY DESIGN

### Baseline measurements

At baseline a number of parameters will be assessed: Vital signs (blood pressure, pulse, respirations and temperature); weight (in kilograms, without shoes) and height (in cm, without shoes). Also a blood sample will be taken prior to the riboflavin intervention. After the three

### The effect of riboflavin supplementation on *Faecalibacterium prausnitzii* in Crohn's disease

weeks of intervention this blood sample will be repeated. Laboratory analysis will take place of a standard set of parameters routinely determined in IBD patients. The blood sample consists of: ALAT, ASAT, Alkaline phosphatase, amylase, BSE, CRP, ferritin, GGT, Hb, Ht, creatinine, leukocyte count, MCV, trombocyte count, TYBC and iron (9.0 ml of blood (EDTA 4.0 ml and Lithium Heparine 5.0 ml)). Additionally, both before and after the intervention two extra blood tubes (1 plasma and 1 serum tube) will be drawn for storage (2 x 10 ml = 20 ml blood). This blood will be used to determine a number of different biomarkers for permeability: I-FABP (plasma) and SM-22 (serum). The above means that 29 ml of blood will be drawn per time point. Also an urine sample will be collected. Claudin-3, a marker of permeability, will be measured in the urine.

	Baseline	Wk 1 of riboflavin intervention	Wk 2 of riboflavin intervention	Wk 3 of riboflavin intervention	2 wk after the intervention
Informed consent	X				
Clinical visit	X			X 	
HB-index 	X			X 	
IBD-Q questionnaire	X			X 	
Bloodsample	X			X 	
Urine sample	X 		X 	X 	X
Chroom-EDTA test	X			X 	
Faeces sample	X 		X 	X 	X
Separate faeces sample for calprotectin	X			X 	

*Table 1: Schedule of activities for participating patients: 1). HB - Index: Harvey Bradshaw Index; 2). Faeces and urine sample are taken at two time points prior to the riboflavin intervention. There will be at least six days between both time points. 3). Faeces and urine collected on day 10 after starting the intervention. 4). These measurements will take place on the last day of the riboflavin intervention.*

## The effect of riboflavin supplementation on *Faecalibacterium prausnitzii* in Crohn's disease

At two time points a Chroom-EDTA permeability test will take place to assess the permeability of the gut. The Chroom-EDTA test is used in this hospital before in the (by the ethical committee approved) COLIPI clinical trial ('*Identification of predictive parameters for colitis in melanoma patients treated with ipilimumab*' (METc 2012/085)). Participants will be asked to come to the hospital fasted (without breakfast). Prior to drinking the Chroom-EDTA a pregnancy test will be performed in the urine of all female participants (dipstick test). When the pregnancy test is negative, participants will be asked to drink the Chroom-EDTA during the clinical visit. After drinking the Chroom-EDTA participants will remain fasted for an additional two hours. Hereafter participants will be asked to collect urine during 24 hours (see 'proefpersoneninformatie' for detailed instructions). Additionally, a Harvey Bradshaw Index (HBI) will be taken before and after the riboflavin intervention to quantify the severity of the symptoms of the disease, and to evaluate if any clinical relevant improvement occurs (see attachment 1). The HBI is based on five items: general wellbeing (0 = very well, 1 = slightly below average, 2 = poor, 3 = very poor, 4 = terrible); abdominal pain (0 = none, 1 = mild, 2 = moderate, 3 = severe); number of liquid stools per day; abdominal mass (0 = none, 1 = dubious, 2 = definite, 3 = tender); and complications (arthralgia, uveitis, erythema nodosum, aphthous ulcers, pyoderma gangrenosum, anal fissure, new fistula and abscess (complications, score 1 per item)). A total score of less than 5 is generally considered to represent clinical remission. A score of 5 – 7 is considered as mild disease, 8 – 16 as moderate disease and > 16 as severe disease. (24)

### Riboflavin intervention

The study is designed in such a way that the participants are their own controls (control period). After signing the informed consent patients are asked to collect a stool sample to measure the amount of *Faecalibacterium prausnitzii* (*F. prausnitzii*). After 6 days a second sample is requested, where after the intervention with riboflavin can commence. These two samples prior to the riboflavin intervention are meant to give a reflection of the amount of *F. prausnitzii* without stimulation and the mean individual degree of fluctuation (control period). During the riboflavin intervention period, the participant is asked to take one capsule of riboflavin (100 mg) per day. After ten days, and on the final day of taking the supplement another stool sample will be requested (see check lists). This to measure the effect of riboflavin on the amount of *F. prausnitzii*. On the second clinical visit patients will be asked to bring the riboflavin container. The capsules will be counted as a control to assess if the patient has followed the dosing instructions. The riboflavin supplement is then stopped, and another stool sample will be requested two weeks after stopping. Furthermore, the changes in bacterial composition, and bacterial products (i.e. butyrate) before and after the riboflavin intervention will be assessed. The stool samples will be tested on *F. prausnitzii* and other (butyrate producing) bacteria, using fluorescent in situ hybridization (FISH) with specific probes. On two days (day 6 and day 28, see checklist) patients will be asked to divide de faeces over two containers instead of one. This extra container on these days contains a glycerol (20%), cysteine and pbs buffer (10 ml). This is used to preserve the bacteria for

## The effect of riboflavin supplementation on *Faecalibacterium prausnitzii* in Crohn's disease

analysis of the electrical current and culturing experiments. The concentration of certain fatty acids in the stool will be measured. In this butyrate is of particular interest. In addition, a portion of the faeces sample will be stored, for microbiome analysis. Microbiota will be analysed with pyrosequencing. All findings in the area of intestinal wellbeing, frequency of defecation, and the consistency of the faeces will be recorded in a questionnaire on two time points (IBD-Q, see F1, 'vragenlijst IBD-Q'). Also faeces will be collected for analysis of the faecal calprotectin. Faecal calprotectin is a neutrophilic protein in faeces, and considered to be a useful non-invasive tool, for differentiating IBD from non-organic disease. Also it is shown that repeated measurements of faecal calprotectin can predict disease course. (25) This measurement will be performed twice: at baseline and on the last day of the riboflavin intervention. For the complete schedule of activities and the different time points see Table 1 and the checklist of the participants. On two timepoints (day 17 and day 42) all samples will be collected (either with car) or participants will bring the samples to the hospital themselves.

## 4. STUDY POPULATION

### 4.1 Population (base)

The study population consists of 84 participants in total. All participants have been diagnosed with Crohn's disease prior to inclusion. Two groups will be formed based on severity of disease. Disease activity will be primarily determined by faecal calprotectin. Participants in the first group (group 1) have a low calprotectin and are considered to be in remission. Participants in the second group (group 2) have a high calprotectin, and are considered to have (moderate) active disease. 42 participants will be included per group. The groups are described in detail below (Chapter 4.2). Of all 84 participants, the effect of the riboflavin intervention will be evaluated by analysing different samples at different time points (blood, urine, faeces, and a clinical severity disease score (HB-index) and the validated IBD-Q questionnaire).

### 4.2 Inclusion criteria

#### Group 1 (n=42)

- Patients diagnosed with Crohn's disease in remission (calprotectin < 200 µg/g)
- Age 18-65 years

#### Group 2 (n=42)

- Patients diagnosed with Crohn's disease with active disease (calprotectin > 200 µg/g)
- Age 18-65 years

Concomitant medication for Crohn's disease is allowed in all groups.

## The effect of riboflavin supplementation on *Faecalibacterium prausnitzii* in Crohn's disease

### 4.3 Exclusion criteria

A potential subject who meets any of the following criteria will be excluded from participation in this study:

- Swallowing disorders
- Pregnancy and lactation
- Use of antibiotic drugs, probiotics (i.e. Yakult, Vifit, Activia etc) or specific prebiotic supplements in the 3 weeks prior to the riboflavin intervention (for a list of probiotic, prebiotic and other supplements see attachment 2)
- Use of Methotrexate drugs
- Colonoscopy and colon cleansing in last 3 months (26)
- Use of a vitamin B2 supplement, or multivitamin complexes containing vitamin B (i.e. vitamin B-complex) in the 3 weeks prior to the riboflavin intervention
- Severe Crohn's disease (HBI > 12)

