### 5.2 Use of co-intervention (if applicable)

When patients use antibiotic drugs, probiotics (i.e. Yakult, Vifit, Activia etc), specific prebiotic supplements or specific vitamin supplements during the 3 weeks prior to the start of the riboflavin intervention they cannot participate in the study (see exclusion criteria). In addition participants are asked to refrain from specific supplements during the study period (see 'proefpersoneninformatie', attachment 8). In addition, participants are asked to refrain from alcohol, two days before test days. Participants are asked to refrain from smoking during the study period. Also participants are asked to refrain from intensive physical activity on the day before a test days.

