## 8.3 Study procedures

Standard faeces samples (five time points: day 0, day 6, day 17, day 28 and day 42) will be divided into three fractions:

- The first fraction (0.5 gram) will be fixed with 4% paraformaldehyde in Phosphate Buffered Saline (PBS) and used for FISH analysis with specific probes. (29)
- The second fraction (100 µgram) will be used for the analysis of volatile fatty acids.
- The third fraction (0.5 gram) will be stored for microbiome analysis by Next Generation Sequencing (microbiome analysis, by 16S RNA sequencing and MiSeq Illumina).
- The remainder is retained for dry weight determination, pH analysis and lactate analysis.

Faeces samples on glycerol, cysteine and PBS mix (two time points: day 6 en day 28):

-These samples will be used for the electrical current measurements of faeces and cell culturing experiments.

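### The 3-week washout is counted back from riboflavin start, not from the first control stool, so the two control stools have unequal washout (about 14 and 20 days)

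*Combined protocol and SAP*

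**What the plan says.** Section 4.3 sets a three-week look-back for antibiotics, probiotics and prebiotics, in the words "specific prebiotic supplements in the 3 weeks prior to the riboflavin intervention". It sets the same look-back for vitamin B2 and for "multivitamin complexes containing vitamin B (i.e. vitamin B-complex) in the 3 weeks prior to the riboflavin intervention". Section 5.2 restates the rule: patients who use these products "during the 3 weeks prior to the start of the riboflavin intervention they cannot participate in the study". No section sets a window before the first control stool.

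Section 8.3 schedules standard stools at "five time points: day 0, day 6, day 17, day 28 and day 42". Section 3 puts the first capsule after both control stools: "After 6 days a second sample is requested, where after the intervention with riboflavin can commence". It gives the purpose of the control stools as follows: "These two samples prior to the riboflavin intervention are meant to give a reflection of the amount of" *F. prausnitzii* without stimulation, and of its fluctuation within the patient. The footnotes to Table 1 set a minimum of six days between the two control stools, with no maximum, and place the mid-intervention stool on day 10 of riboflavin.

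Section 8.2 states that there is no randomisation and that patients are their own controls. Section 10 compares the control period with day 28 by a paired Wilcoxon test. It does not say whether the control value is day 0, day 6 or their mean.

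**The concern.** A washout protects a measurement only if it is complete when the measurement is taken. Here the three weeks are complete at the first capsule, but the measurements that need protection are the control stools, which come first. They are the only comparator in the trial.

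Two things follow. First, any change still under way after an exposure continues between the control stools and day 28, and the paired test cannot separate it from an effect of riboflavin. Second, the two control stools lie at different distances from the last exposure, so part of the difference between them may be carry-over, although the protocol means to read that difference as individual fluctuation.

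The direction depends on the product. If antibiotics had suppressed *F. prausnitzii*, regrowth would raise the before-after difference. By the protocol's rationale (Section 1), riboflavin raises *F. prausnitzii*, and inulin raised it from 10.3% to 14.5%. Carry-over from vitamin B2 or an inulin-type prebiotic would therefore leave the control value high and hide an effect. The documents give no direction for probiotics.

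**Working it through.** **1. The plan's own sample size.** Inputs from Section 4.4: expected increase 2.45×10⁸ per gram, SD 6.22×10⁸, one-sided alpha 0.05, power 0.80. The standardised effect is 2.45/6.22 = 0.394. The normal approximation, ((1.645 + 0.842)/0.394)², gives 40. The exact paired t calculation gives power 0.798 at n = 41 and 0.807 at n = 42, so 42 is reproduced. The washout is not an input, so a change to it leaves 42 per group unchanged.

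**2. Day of riboflavin start.** Study day 17 is day 10 of riboflavin, so the start is about day 17 − 10 = 7. Conventions for counting days put it between day 6 and day 8.

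**3. Guaranteed interval since last exposure.** The latest permitted exposure is on day (start − 21), so the interval at a stool is 21 − (start day − stool day).

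| Stool | Start day 7 | Range, start day 8 to 6 |
|---|---|---|
| Day 0 | 21 − 7 = 14 days | 13 to 15 |
| Day 6 | 21 − 1 = 20 days | 19 to 21 |
| Mean of both | 17 days | 16 to 18 |
| Day 28 | 21 + 21 = 42 days | 41 to 43 |

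**4. Longer gaps between control stools.** If riboflavin starts the day after the second stool, the interval at the first stool is 21 − (gap + 1). A 10-day gap leaves 10 days and a 13-day gap leaves 7.

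**5. Effect of counting from day 0.** The guaranteed interval at day 0 rises from 14 to 21 days, at day 6 from 20 to 27, and at riboflavin start from 21 to about 28.

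**6. How much carry-over that would remove.** The documents give no recovery speed. As an assumption, let a disturbance fade as exp(−t/τ), with τ = 7, 14 or 28 days. The bias, as a share of the initial disturbance, is its value at the control stool minus its value at day 28. For τ = 14 and the day-0 stool this is exp(−14/14) − exp(−42/14) = 0.368 − 0.050 = 0.318.

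| τ (days) | Now, day 0 | Now, mean | Now, day 6 | Counted from day 0, day 0 as control | Share of bias left, exp(−7/τ) |
|---|---|---|---|---|---|
| 7 | 0.133 | 0.094 | 0.055 | 0.049 | 37% |
| 14 | 0.318 | 0.254 | 0.190 | 0.193 | 61% |
| 28 | 0.383 | 0.325 | 0.266 | 0.299 | 78% |

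For a patient at the edge of the rule, counting from day 0 leaves 37% to 78% of the bias. Using day 6 as the control under the present rule does about as well as counting from day 0 and using the day-0 stool.

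**7. Sensitivity of the test to drift.** As an illustration, assume no riboflavin effect, n = 42, SD 6.22×10⁸ and a one-sided paired t test. A mean upward drift over the whole group of 10%, 25% or 50% of the planned 2.45×10⁸ then gives a false-positive rate of about 8%, 15% or 35%, instead of 5%. The documents do not show that a drift of any such size would occur, and these rates do not measure what the change removes.

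**The case against.** The protocol asks for three clear weeks before riboflavin and never promises three weeks before the control stools, so no stated rule is broken. The day-6 stool falls short of three weeks by about one day, and only day 0 is short by a week. If day 6 is the comparator, little of the defect remains. The patients concerned are only those whose last exposure falls in about one extra week, and that may be few. Step 6 also shows that the change leaves a good part of the bias. The larger weakness, an uncontrolled before-after comparison, is a deliberate feature of the design, and no washout rule cures it.

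Most of this stands. It limits the point to a modest improvement. It does not remove it, because Section 10 does not choose day 6, the gap between control stools has no upper limit, and nothing else in the plan protects the control values from carry-over.

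A reader might infer that recovery after all of these exposures would be credited to riboflavin. The documents do not support that: they give no recovery time for any product, and by their own rationale carry-over from vitamin B2 or inulin would work against riboflavin. A reader might also put a figure on the inflation of the error rate. That would need the share exposed and the size of recovery, and the documents give neither.

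**Conclusion.** The point holds as a matter of timing. Sections 4.3 and 5.2 tie the washout to the first capsule, so a patient who just meets the rule gives control stools about 14 and 20 days after last exposure, and the first interval is shorter if the control stools are more than six days apart. Carry-over can bias the only comparison in the trial, in a direction that differs by product, so the net sign is unknown.

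The size is unknown as well. The shortfall is a week if day 0 is the comparator, about four days on average if the mean of both stools is, and about one day if day 6 is. The day counts rest on riboflavin starting on about day 7. The shares in step 6 rest on an assumed exponential recovery. The sample size is unaffected. This is a cheap improvement and not a flaw that invalidates the analysis.

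**What to change.** In Sections 4.3 and 5.2, keep the same three weeks and the same list of products, but count the period back from the first control stool (day 0) instead of from riboflavin start.

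For patients already enrolled with an exposure between day −21 and day 0, keep them in the primary analysis and add one sensitivity analysis, either without them or with day 6 as their control value. This needs the date of last exposure for each patient, which the protocol does not say is recorded.

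The eligibility wording should stop at the first control stool. An exclusion criterion cannot be checked against future use, and Section 5.2 already covers supplements after entry: "participants are asked to refrain from specific supplements during the study period".

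The cost is a wording amendment, and a first stool about one week later for a few candidates. No procedure is added, and 42 per group stands. The change reduces carry-over without removing it, and the report should say so.

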### 4.4 Sample size calculation

The primary objective in this study is to investigate whether the number of *F. prausnitzii* increases as result of a riboflavin intervention in patients with Crohn's disease. A power calculation has been performed ([name]). First the mean increase in *F. prausnitzii* as seen in the healthy volunteer riboflavin pilot study was calculated. In this study bacteria were measured per grams of faeces. The amount of bacteria were measured with FISH. The mean increase was  $6.14 \cdot 10^8$  bacteria per gram of faeces per volunteer (SD:  $1.56 \cdot 10^9$ ). In an article of Swidsinski et al 2008 the number of *F. prausnitzii* bacteria in the bowel was measured in 82 Crohn's disease patients using FISH. (27) The mean of *F. prausnitzii* was  $5.6 \cdot 10^9$  bacteria / ml of faeces (SD:  $5.9 \cdot 10^9$ ). In this same article, it is shown that the mean of *F. prausnitzii* in healthy volunteers (n=32) is much higher:  $14.9 \cdot 10^9$  bacteria / ml faeces (SD:  $4.5 \cdot 10^9$ ). In the article of Swidsinski, the number of *F. prausnitzii* is roughly 2.5 times higher in the healthy group as opposed to the group with Crohn's disease. We expect that the same ratio of *F. prausnitzii* between healthy volunteers and Crohn's disease patients will be the case in our population. A similar increase as seen in the healthy volunteer group is hypothesized to take place after the riboflavin intervention. This results in an expected mean increase of *F. prausnitzii* of  $2.45 \cdot 10^8$  bacteria / grams of faeces in our Crohn's disease group (SD:  $6.22 \cdot 10^8$ ). With a one sided test, with a power of 0.80 and an alpha of 0.05, this will result in a sample size of 42 patients for the group in remission. Since we want to study the effect in two experimental groups (one group in remission, and one group with active disease), 84 patients will be recruited.

In this study an adaptive design will be used. When the first 12 patients in the disease in remission group are included and have completed the study procedures, the collected faeces samples will be analyzed. The number of *F. prausnitzii* with FISH will be determined and compared on different timepoints (primary endpoint). Also the ratio of enterobacteriaceae / *F. prausnitzii* will be determined. When the increase of the *F. prausnitzii* bacteria is less than

**The effect of riboflavin supplementation on *Faecalibacterium prausnitzii* in Crohn's disease**

the increase seen in the healthy volunteer study, we will reassess the performed power calculation. Also safety aspects will be taken into account continuously. The HB-index and the reported adverse events will be noted. If there are indications to believe that the safety of the participants are at risk, the study will be suspended, and we will reassess continuing the study.

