### 9.2 AEs, SAEs and SUSARs

#### 9.2.1 Adverse events (AEs)

Adverse events are defined as any undesirable experience occurring to a subject during the study, whether or not considered related to the investigational product. All adverse events reported spontaneously by the subject or observed by the investigator or his staff will be recorded.

The collection of faeces and urine samples entails no risks for the subjects. The Harvey Bradshaw Index can be determined by taking a short questionnaire (5 items). The IBD-Q is a validated questionnaire used to measure the influence of the inflammatory bowel disease on the quality of life and the impact of the disease.

No side effects of Chroom-EDTA have been reported.

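### Safety review is called continuous, but no disease-activity score or adverse-event question is scheduled between baseline and the last dosing day, or in the 14 days after stopping

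*Combined protocol and SAP*

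**What the plan says.** Section 4.4 (Sample size calculation) ends with a safety provision naming two sources: "Also safety aspects will be taken into account continuously. The HB-index and the reported adverse events will be noted". The action tied to it is at study level: "If there are indications to believe that the safety of the participants are at risk, the study will be suspended", followed by reassessment. Section 8.7 repeats the suspension provision without naming a data source.

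Section 3 gives the HBI two readings: "a Harvey Bradshaw Index (HBI) will be taken before and after the riboflavin intervention". Table 1 marks the clinical visit, HBI, IBD-Q, blood sample and calprotectin at baseline and in week 3 only, and its note 4 fixes the week-3 mark: "These measurements will take place on the last day of the riboflavin intervention". The week 1 and week 2 columns hold no clinical item. In the column for two weeks after the intervention only urine and faeces are marked, and the text agrees: "another stool sample will be requested two weeks after stopping". Section 3 describes the hand-over of samples as follows: "On two timepoints (day 17 and day 42) all samples will be collected (either with car", or else brought in by the participant. No assessment is attached to either hand-over.

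On adverse events, section 9.2.1 says: "All adverse events reported spontaneously by the subject or observed by the investigator or his staff will be recorded". Section 9.4 follows known events until they resolve or stabilise and has serious events reported up to the end of the study. Section 8.1.2 lists adverse events among the secondary parameters. Table 1 has no adverse-event row.

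**The concern.** A review can be no more continuous than the data that reach it. One of the two named sources, the HBI, has no reading between baseline and the last dosing day and none after it. The other is passive. The schedule therefore does not deliver regular information from each patient during dosing or after stopping, which is one natural meaning of the word in section 4.4.

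What is at stake is ascertainment. The study is unblinded and has no control group, so its adverse-event count will be read on its own. A low count may mean that few events occurred, or that patients with a known fluctuating disease did not think a few bad days worth reporting. The plan as written cannot separate the two. The same holds for any statement on disease activity in the two weeks after riboflavin stops, where nothing clinical is collected.

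**Working it through.** The plan gives no figure on this point. The sample size of 42 in section 4.4 does not enter the argument and does not change. The check sets the schedule against the safety statement and counts days.

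**1. Table 1, clinical content only**

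| Item | Baseline | Week 1 | Week 2 | Week 3 (last dosing day) | Two weeks after |
|---|---|---|---|---|---|
| Clinical visit | yes | – | – | yes | – |
| HBI | yes | – | – | yes | – |
| IBD-Q | yes | – | – | yes | – |
| Calprotectin | yes | – | – | yes | – |
| Adverse-event question | no row | no row | no row | no row | no row |

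Scheduled HBIs after the first dose and before the last dosing day: 0. After stopping: 0.

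**2. Day count**

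- Standard stool sampling in section 8.3 has "five time points: day 0, day 6, day 17, day 28 and day 42".
- Table 1, note 3, puts the mid-treatment sample on day 10 of the intervention. If day 17 is dosing day 10, the first dose is on day 17 − 9 = 8.
- Day 28 is then dosing day 28 − 8 + 1 = 21, which agrees with the 21 daily capsules in section 7.7.
- Dosing days before the single on-treatment HBI: 21 − 1 = 20.
- The day of the baseline visit is not stated. Assuming it falls between day 0 and day 7, the interval between the two HBIs is between 28 − 7 = 21 and 28 − 0 = 28 days.
- After the last HBI: 42 − 28 = 14 days, and 14/42 = 0.33 of the schedule.

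**3. Does the last-day HBI look back over the interval?** No. In Attachment 1 the well-being, pain and stool items refer to the day before.

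**4. Does another section fill the gap?** Sections 9.2.1 and 9.4 keep a channel open throughout the study, but the patient or staff must first raise the event. Section 9.5 (safety board), section 12.2 (monitoring) and section 8.4.1 (specific withdrawal criteria) are all marked not applicable. No section schedules an adverse-event enquiry.

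**5. Effect of using the existing hand-overs.** With a form on days 17 and 42, the intervals between scheduled questions become 10 to 17 days (17 − 7 to 17 − 0), 28 − 17 = 11 days and 42 − 28 = 14 days. The longest interval falls from 21–28 days to 14–17 days, and the final 14 days end with an assessment instead of none.

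**The case against.** The strongest reply is that section 4.4 speaks of suspending the study, not of stopping an individual patient. HBI and adverse-event data accrue across up to 84 patients, so ongoing review across patients is a fair reading of the word. That stands. Section 4.4 does not say so, however, and gives no review interval. Under that reading the review is still fed by one on-treatment HBI per patient and by unprompted reports.

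A second reply is proportionality. The intervention is 21 days of a supplement sold without prescription, and section 7.4 cites a study of 49 patients on a higher dose with no short-term side effects. This argues against extra visits. It weighs little against a form sent with samples that are being handed over anyway.

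A third reply is that the participant information, checklists and case record forms are not part of the document and may contain reporting instructions or prompts. That cannot be excluded. If they do, Table 1 and section 9.2.1 should say so.

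Some stronger conclusions are tempting but not supported:

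- A reader might infer that worsening goes unseen. Sections 9.2.1 and 9.4 contradict this: a flare that is reported at any time in the study is recorded and followed.
- A reader might object that the last-day HBI comes too late to guide that patient's treatment. Section 4.4 makes no patient-level claim.
- A reader might say the plan will wrongly report no rebound after stopping. Secondary objective 3 does not mention rebound or activity after withdrawal.
- A reader might cite the early look at 12 remission patients, where zero events still allow a rate up to 1 − 0.05^(1/12) = 0.22 (one-sided 95% bound). That is a property of 12 patients, not a measure of the schedule gap, and section 4.4 does not confine safety review to those 12.

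**Conclusion.** The point holds as a mismatch between the safety wording and the schedule, with a consequence for ascertainment. No disease-activity assessment or adverse-event enquiry is scheduled for 21 to 28 days up to the last dosing day, a span that includes the first 20 of 21 dosing days, or in the 14 days after it. In those periods detection of worsening depends on spontaneous reports, so adverse events may be under-counted.

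The extent of under-counting cannot be estimated, because the documents give no rate of events or of reporting. The day counts assume that day 17 is dosing day 10 and that the baseline visit falls between day 0 and day 7. No power, alpha or sample-size figure is affected, and the documents do not show that participants are unsafe. The point merits action mainly because the remedy is cheap.

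**What to change.** Add a row to Table 1 for a short paper form returned with the samples on day 17 and day 42. It should hold one standard open adverse-event question covering the time since the last contact, and the patient-reported HBI items. Report the latter as a partial score, kept apart from the full HBI, because abdominal mass needs examination. Paper is needed because a hand-over by car may involve no study staff.

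Reconcile the word 'continuously' in section 4.4, and the matching suspension provision in section 8.7, with the schedule as it will be carried out, including whether review is across patients and how often accrued data are read. If no form is added, describe the review as it will occur and state in section 9.2.1 that adverse-event data outside the two visits come from spontaneous reports only.

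The cost is two forms per patient, 2 × 84 = 168 in all, with their data entry and a slight burden on patients. No visit is added. Two further readings would still not be continuous, so the wording needs attention either way. No clinical threshold, stopping rule or extra calprotectin assay is proposed.
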